#### **CLINICAL LABORATORY DETERMINATIONS**

Blood and urine samples will be collected for Clinical Laboratory Determinations at the Screening visit and at all subsequent clinic visit except Visit 2, 3 (Week 0, 4) (DB phase: Visit 4, 5, 6, 7 and early discontinuation and OLE phase; Visit 8, 9, 10 and early discontinuation).

Clinical laboratory tests to be performed, including hematology, chemistry, and urinalysis, are summarized in Table 1. Subjects should be in a seated or supine position during blood collection.

**Table 1. Clinical Laboratory Tests**

Category	Parameters
Hematology	hematocrit, hemoglobin, platelets, RBC count, and WBC count with differential (bands, basophils, eosinophils, lymphocytes, monocytes, neutrophils), INR (only for patients taking warfarin)
Chemistry	
Electrolytes	chloride, potassium, sodium
Liver function tests	alanine aminotransferase, alkaline phosphatase, aspartate aminotransferase, direct bilirubin, total bilirubin
Renal function parameters	blood urea/blood urea nitrogen, creatinine
Other	albumin, calcium, cholesterol, creatine kinase, globulin, glucose, lactate dehydrogenase, phosphorus, total protein, triglycerides, uric acid, HbA1c
Urinalysis	casts, crystals, epithelial cells, glucose, ketones, occult blood, pH, protein, RBCs, specific gravity, WBCs
Others (only at Screening)	hepatitis B surface antigen, thyroid profile (TSH and free T4), vitamin B-12, folate

RBC = red blood cell, WBC = white blood cell, TSH = thyroid stimulating hormone

A laboratory abnormality may meet the criteria to qualify as an AE as described in this protocol (see Adverse Events and Other Events of Interest [Section 9.5.1.5]) and the CRF Completion Guidelines. In these instances, the AE corresponding to the laboratory abnormality will be recorded on the appropriate CRF.

For laboratory abnormalities meeting the criteria of SAEs (see Serious Adverse Events and Other Events of Interest [Sections 9.5.1.5]), the site must fax or email the SAE report including the laboratory report (as regionally required) to the sponsor using the SAE form (see Reporting of Serious Adverse Events [Section 9.5.4.1]).

## VITAL SIGNS AND WEIGHT MEASUREMENTS

Vital signs (i.e., systolic and diastolic blood pressure (BP) [mmHg], pulse [beats per minute]), and weight [kg] will be obtained by a validated method at all clinic visits of DB and OLE phase (Table 2 and Table 3). BP will be measured by a qualified instrument in the supine position (only at Screening and Visit 2 (Week 0)) and in the sitting position (at all visits). Automated measurement is available. All BP measurements should be performed on the same arm, preferably by the same person. Weight will be recorded.

## ELECTROCARDIOGRAMS

A 12-lead ECG will be performed at Screening and at the Visit 3, 4, 5, 6, 7 and early discontinuation of DB phase, and visit 8, 9 10 and early discontinuation of OLE phase. The ECG

will be a complete, standardized 12-lead recording. Electrocardiograms will be properly mounted and evaluated by the investigator or a qualified consultant.

An ECG abnormality may meet the criteria of an AE as described in this protocol (see Adverse Events and Other Events of Interest [Section 9.5.1.5]) and the CRF Completion Guidelines. In these instances, the AE corresponding to the ECG abnormality will be recorded on the Adverse Events CRF.

For ECG abnormalities meeting criteria of an SAE (see Serious Adverse Events and Other Events of Interest [Section 9.5.1.5]), the site must fax or email the SAE report including the ECG report to the sponsor using the SAE form (see Reporting of Serious Adverse Events [Section 9.5.4.1]).

#### **PREGNANCY TEST**

Pregnancy test will be performed at all visits only for female subjects of childbearing potential (pre-menopausal women or women who are amenorrhea for less than 12 months from the last menstrual cycle only). A serum  $\beta$ -hCG test will be performed at Screening, and urine test at all other visits.

## 9.5.2 Schedule of Procedures/Assessments

### 9.5.2.1 Schedule of Procedures/Assessments

**Table 2. Schedule of Procedures/Assessments in Study E2020-K082-418: <Core Study>**

Phase	Screening		Double-Blind					
	Screening	Baseline	Titration	Maintenance				Early Discontinuation
Period	1	2	3	4	5	6	7	
Visit	1	2	3	4	5	6	7	Early Discontinuation
Duration (Weeks)		Week 0	Week 4	Week 6 i)	Week 12	Week 18	Week 24	
Duration (days)	-28 to -7	0	28-35	35-49	77-91	119-133	161-168	Early Discontinuation
Informed Consent a)	X							
Inclusion/Exclusion Criteria	X	X						
Demography/Medical History	X							
Diagnosis (NINDS-AIREN)	X							
Hachinski Ischemia Scale	X							
Neurological Examination	X							
Cranial MRI or CT b)	X							
CDR	X							
Prior and Concomitant Medications	X	X	X	X	X	X	X	X
Randomization		X						
Dispense Study Drug		X	X	X	X	X		
Study Drug Compliance			X	X	X	X	X	X
Return Unused Study Medication			X	X	X	X	X	X
Efficacy								
MMSE c)	X	X	X		X	X	X	X
ADAS-cog c)		X	X		X	X	X	X
Executive function test c)		X			X		X	X
CIBIC-plus								
CIBIS d)		X						
CIBIC d)			X		X		X	X
Safety								
Vital Signs e)	X	X	X	X	X	X	X	X
12-lead ECG	X		X	X	X	X	X	X
Clinical Laboratory Determinations f)	X			X	X	X	X	X
Pregnancy Test (females only) g)	X	X		X	X	X	X	X
Adverse Events h)	X	X	X	X	X	X	X	X

- a) If the patient is unable to provide written informed consent, written consent must be obtained from the patient's representative and verbal assent must be obtained from the patient. The caregiver must separately provide IC for his/her own participation in the study.
- b) To be obtained as part of the Screening activities, if an MRI or CT was not obtained within the past 6 months. If obtained as part of Screening, a scan must be obtained at least 7 days prior to the baseline visit.
- c) Every test for one subject should administered by one rater throughout the core study (Baseline and DB phase).
- d) CIBIS and every CIBIC for one subject should be evaluated by one rater throughout the study. Clinical information about the subject from any source can be used for the CIBIS, but not at any other time for the CIBIC during the study. The rater will refer to the CIBIS to complete the CIBIC.
- e) Blood pressure, radial pulse, and Weight, all visits.
- f) All clinical laboratory tests will include hematology, clinical chemistry and urinalysis. Additionally, at the Screening visit only, assessments of serum vitamin B12, folate levels, thyroid profile and hepatitis B and C titers will be obtained. INR only for patients taking warfarin.
- g) To perform only for pre-menopausal women or women who are amenorrhea for less than 12 months from the last menstrual cycle. Serum at Screening, urine at other visits.
- h) Adverse events will be collected from the time subject signs informed consent form through the last visit. Serious adverse events will be collected through the last visit and for 30 days after study termination.
- i) There should be an interval of 1 week or longer between Week 4 (Visit 3) and Week 6 (Visit 4).

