## 5 ETHICS

### 5.1 INSTITUTIONAL REVIEW BOARDS/INDEPENDENT ETHICS COMMITTEES

The protocol, informed consent form (ICF), and appropriate related documents must be reviewed and approved by an Institutional Review Board (IRB) or Independent Ethics Committee (IEC) constituted and functioning in accordance with ICH E6 (Good Clinical Practice), Section 3, and any local regulations. Any protocol amendment or revision to the ICF will be resubmitted to the IRB/IEC for review and approval, except for changes involving only logistical or administrative aspects of the study (e.g., change in CRA[s], change of telephone number[s]). Documentation of IRB/IEC compliance with the ICH E6 and any local regulations regarding constitution and review conduct will be provided to the sponsor.

A signed letter of study approval from the IRB/IEC chairman must be sent to the principal investigator with a copy to the sponsor before study start and the release of any study drug to the site by the sponsor or its designee (ICH E6, Section 4.4). If the IRB/IEC decides to suspend or terminate the study, the investigator will immediately send the notice of study suspension or termination by the IRB/IEC to the sponsor.

Study progress is to be reported to IRB/IECs annually (or as required) by the investigator or sponsor, depending on local regulatory obligations. If the investigator is required to report to the IRB/IEC, he/she will forward a copy to the sponsor at the time of each periodic report. The investigator(s) or the sponsor will submit, depending on local regulations, periodic reports and inform the IRB/IEC of any reportable adverse events (AEs) per ICH guidelines and local IRB/IEC standards of practice. Upon completion of the study, the investigator will provide the IRB/IEC with a brief report of the outcome of the study, if required.

At the end of the study, the sponsor should notify the IRB/IEC within the period in accordance with the IRB/IEC's requirements.

In the case of early termination/temporary halt of the study, the investigator should notify the IRB/IEC within the period in accordance with the IRB/IEC's requirements and a detailed written explanation of the reasons for the termination/halt should be given.

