### **9.3.3 Removal of Subjects from Therapy or Assessment**

#### **1) Scheduled Termination**

The patient will be considered to have completed the DB phase after 24 weeks of double-blind treatment and completion of the Week 24 visit procedures. Patients who have completed the DB phase can be enrolled in the OLE phase. The patient will be considered to have completed the OLE phase after 24 weeks of open-label treatment and completion of the Week 24 visit procedures. Upon completion of DB phase or OLE phase, and after resolution of any AEs or laboratory abnormalities that may be present on the last study day, the patient will be considered to have completed the study.

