#### **2) Unscheduled Termination or Removal of Patients from the Study**

In accordance with the Declaration of Helsinki, patients have the right to withdraw from the study at any time and for any reason. The principal investigator (PI) and/or the sponsor have the right to withdraw a patient from the study for any of the following reasons:

1. Adverse event (AE)
2. At the request of the patient, PI, or Sponsor, whether for administrative or other reasons
3. Protocol violation or unreliable, disruptive behavior
4. Patients could be considered for withdrawal at any time from the study for lack of efficacy or evidence of no therapeutic benefit.
5. Patients could be considered for withdrawal when the patients receive prohibited/restricted concomitant medication.

If a patient decides to discontinue participation, or is removed from the study prior to completion, the final discharge procedures should be conducted. Specific events leading to discontinuation and any related test results will be recorded and explained in the CRF.

If a patient decides to discontinue study medication for any reason, he/she will be instructed to immediately notify the PI. In such cases, an early termination visit must be scheduled as soon as possible, preferably within 1 to 3 days following discontinuation of study medication.

The date and time of the last drug dose and all observations collected up to the time of termination will be recorded in the source document and the corresponding CRF along with the reason for termination. Procedures at discharge will be conducted, if possible, as described under Scheduled Termination.

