### 9.5.1.5 Safety Assessments

#### **ADVERSE EVENTS AND OTHER EVENTS OF INTEREST**

An adverse event (AE) is any untoward medical occurrence in a subject or clinical investigation subject administered an investigational product. During clinical studies, adverse event information will be collected after signing of informed consent in order to collect study-associated events. An AE does not necessarily have a causal relationship with the medicinal product. For this study, the study drug(s) is 5 mg donepezil and corresponding matching placebo, as well as donepezil 10 mg and corresponding matching placebo.

The criteria for identifying AEs are:

- Any unfavorable and unintended sign (including an abnormal laboratory finding), symptom, or disease temporally associated with the use of an investigational product, whether or not considered related to the investigational product
- Any new disease or exacerbation of an existing disease
- Any deterioration in nonprotocol-required measurements of a laboratory value or other clinical test (e.g., ECG or x-ray) that results in symptoms, a change in treatment, or discontinuation of study drug
- Recurrence of an intermittent medical condition (e.g., headache) not present pretreatment (Baseline)
- An abnormal laboratory test result should be considered an AE if the identified laboratory abnormality leads to any type of intervention, whether prescribed in the protocol or not.

A laboratory result should be considered by the investigator to be an AE if it:

- Results in the withdrawal of study drug
- Results in withholding of study drug pending some investigational outcome
- Results in an intervention, based on medical evaluation (e.g., potassium supplement for hypokalemia)
- Results in any out of range laboratory value that in the investigator's judgment fulfills the definitions of an AE with regard to the subject's medical profile

All AEs observed during the study will be reported on the CRF. All AEs, regardless of relationship to study drug or procedure, should be collected beginning from the time the subject signs the study ICF through the last visit. Serious AEs will be collected for 30 days after the last dose.

Abnormal laboratory values should not be listed as separate AEs if they are considered to be part of the clinical syndrome that is being reported as an AE. Any laboratory abnormality considered to constitute an AE should be reported on the appropriate CRF.

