**9.5.3 Appropriate ness of Measurements**

All clinical assessments are standard measurements commonly used in studies of dementia associated with cardiovascular disease.

The safety assessments to be performed in this study, including hematology analysis, blood chemistry test, urinalysis, radiologic studies and assessments of AEs, are standard evaluations to ensure subjects safety.

**9.5.4 Reporting of Serious Adverse Events, Pregnancy, and Other Events of Interest****9.5.4.1 Reporting of Serious Adverse Events**

**All SERIOUS ADVERSE EVENTS, regardless of their relationship to study treatment, must be reported on a completed SAE form by email or fax as soon as possible but no later than 1 business day from the date the investigator becomes aware of the event.**

Serious adverse events, regardless of causality assessment, must be collected through the last visit and for 30 days after the subject's last dose. All SAEs must be followed to resolution or, if resolution is unlikely, to stabilization. Any SAE judged by the investigator to be related to the study treatment should be reported to the sponsor regardless of the length of time that has passed since study completion.

**Deaths and life-threatening events should be reported immediately by telephone. The immediate report should be followed up within 1 business day by emailing or faxing the completed SAE form.**

The detailed contact information for reporting of SAEs is provided in the Investigator Study File.

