#### **11.11 DISCONTINUATION OF STUDY**

The sponsor reserves the right to discontinue the study for medical reasons or any other reason at any time. If a study is prematurely terminated or suspended, the sponsor will promptly inform the investigators/institutions and regulatory authorities of the termination or suspension and the reason(s) for the termination or suspension. The IRB/IEC will also be informed promptly and provided the reason(s) for the termination or suspension by the sponsor or by the investigator/institution, as specified by the applicable regulatory requirement(s).

The investigator reserves the right to discontinue the study should his/her judgment so dictate. If the investigator terminates or suspends a study without prior agreement of the sponsor, the investigator should inform the institution where applicable, and the investigator/institution should promptly inform the sponsor and the IRB/IEC and provide the sponsor and the IRB/IEC with a detailed written explanation of the termination or suspension. Study records must be retained as noted above.

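### Does counting the 30-day SAE window from the last dose in one place and from study termination in another require a change to the plan?

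*Protocol*

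**What the plan says.** Four places in the protocol set the end of SAE collection.

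- Section 9.5.1.5 (Adverse Events and Other Events of Interest): "Serious AEs will be collected for 30 days after the last dose".
- Section 9.5.4.1 (Reporting of Serious Adverse Events): SAEs "must be collected through the last visit and for 30 days after the subject's last dose".
- Table 2, footnote h (core study): "Serious adverse events will be collected through the last visit and for 30 days after study termination".
- Table 3, footnote n (open-label extension): the same sentence as in Table 2.

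All four use 30 days; only the starting point differs. Section 9.5.4.1 adds two rules that apply under either starting point. Every SAE is followed until it resolves or stabilises, and an SAE judged related to treatment "should be reported to the sponsor regardless of the length of time that has passed since study completion".

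**The concern.** The protocol nowhere defines study termination, and its text offers more than one date for it.

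- Under Unscheduled Termination in section 9.3.3, a subject who stops medication has an early termination visit, "preferably within 1 to 3 days following discontinuation of study medication". That timing is a preference, not a limit.
- Under Scheduled Termination in the same section, the subject counts as having completed the study only "after resolution of any AEs or laboratory abnormalities that may be present on the last study day". That date has no fixed upper limit.
- Elsewhere, termination refers to the whole trial: section 5.1 speaks of "the notice of study suspension or termination by the IRB/IEC", and section 11.11 begins a rule with "If a study is prematurely terminated or suspended".

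When a site stops collecting SAEs is a matter of conduct. A statistical analysis plan cannot recover an event that was never recorded. If some sites follow the section text and others the schedule footnotes, the period at risk for a recorded SAE would differ between subjects in the same situation. In an elderly population with vascular disease, that deserves a check.

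**Working it through.** There is no sample size, power or error-rate figure to reproduce. The check compares the rules and works out the dates.

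**Inputs.** Window length: 30 days, in all four places. L is the number of days from the last dose to the subject's last visit. Section 9.3.3 prefers L = 1 to 3 for a subject who stops early. For a completer, section 9.4.1 has dosing continue to the Week 24 visit, so L is about 0.

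**Formulas**, in days after the last dose:

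- Section text: collection runs through the last visit and to day 30, so it ends at max(L, 30).
- Footnotes, with termination read as the last visit: it ends at L + 30.
- Gap = L + 30 − max(L, 30) = min(L, 30).

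| L | Section text ends | Footnotes end | Gap |
|---|---|---|---|
| 0 | day 30 | day 30 | 0 days |
| 1 | day 30 | day 31 | 1 day |
| 3 | day 30 | day 33 | 3 days |

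A delayed visit widens the gap by the delay, but on this reading never beyond 30 days.

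**Which reading is natural.** The footnotes belong to a table of one subject's visits, and the phrase comes directly after the reference to the last visit. That points to the end of the subject's participation. The completion rule in section 9.3.3 speaks of completing the study and uses termination only in its heading. A trial-level meaning would not fit a subject's visit schedule.

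**Which events are exposed.** Because L + 30 is never less than max(L, 30), a site following the footnotes collects at least as long as one following the text. No SAE within 30 days of the last dose falls outside either rule. Beyond that point:

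1. SAEs that began earlier are still followed to an outcome (9.5.4.1).
2. New SAEs judged related are reportable whenever they occur (9.5.4.1).
3. Only new SAEs not judged related, starting inside the gap, depend on which rule the site read.

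**Extension entrants.** For a subject who goes on to the extension, Visit 7 is also extension Week 0 (9.5.2.2). AE collection continues on the extension schedule, so the end of the double-blind phase opens no gap.

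**Effect on the analysis.** Section 9.7.1.8 builds its summary tables from treatment-emergent events and lists all others. As the protocol stands, an SAE starting after day 30 off drug would appear in a listing and leave the tabulated incidences unchanged. Randomisation is blocked within site (9.4.3), so a site's reading applies to both arms.

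**The case for a change.** The strongest case for a change is that this is a contradiction on the face of the protocol, in a conduct rule that only the protocol can settle, and that four small wording edits would remove it. Sites do work from schedule tables, the 1-to-3-day visit is only preferred, and on the completion reading the footnote window has no upper limit. On that reading the window would also be longer for subjects with unresolved events, who need not be equally frequent in the two arms.

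The contradiction stands, and so does the point that an analysis plan cannot cure it. The consequence is much weaker. The open-ended reading is not the natural one for a subject's visit schedule, and it could only lengthen collection.

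A related argument is that SAEs with onset after the last dose might reach listings only, so that separate SAE and death tables are needed. How far the treatment-emergent period runs past the last dose, and which safety tables are produced, is commonly left to the statistical analysis plan. Section 9.7.1 defers further analytical detail to that document, so this is not a fault in the protocol.

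An expected number of affected events cannot be given responsibly. The protocol states no SAE rate for this trial, no distribution of visit delays and no hazard after stopping treatment. Any figure would consist mainly of assumptions.

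**Conclusion.** The concern identifies a genuine clerical inconsistency that does not call for a change to the plan. On the subject-level reading the two rules end 0 to 3 days apart at the preferred visit timing, and further apart only if the visit is late. The footnote rule never collects for less time than the text, so the 30 days after the last dose are covered whichever is followed. What could differ is confined to new SAEs not judged related, with onset in that short gap. Their number cannot be computed from the protocol but should be small. Harmonising the wording without altering the 30 days would change no efficacy result, no tabulated safety incidence as section 9.7.1.8 is written, and no conclusion.

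This rests on two assumptions: that sites read study termination as the end of the subject's participation, and that most early termination visits take place near the preferred time. If either fails, some subjects are observed for longer and none for less than 30 days after the last dose.

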**Table 3. Schedule of Procedures/Assessments in Study E2020-K082-418: <OLE phase>**

Phase	Open-label extension				
Period	Titration	Maintenance (Flexible dose)			
Visit	7	8	9	10	Early Discontinuation
Duration (weeks of Core study)	Week 24				
Duration (weeks of OLE phase)	Week 0	Week 6 o)	Week 12	Week 24	
Duration (days of OLE phase)		28-42	77-91	161-175	
Informed Consent j)	X				
Concomitant Medications		X	X	X	X
Dispense Donepezil	X	X	X	X	
Donepezil Compliance		X	X	X	X
Return Unused Study Medication		X	X	X	X
Efficacy					
MMSE		X	X	X	X
Safety					
Vital Signs k)		X	X	X	X
12-lead ECG		X	X	X	X
Clinical Laboratory Determinations l)		X	X	X	X
Pregnancy Test (females only) m)		X	X	X	X
Adverse Events n)		X	X	X	X

j) Subjects who completed the DB phase can be enrolled in this phase. Written informed consent must be obtained again.

k) Blood pressure, radial pulse, and weight, all visits.

l) All clinical laboratory tests will include hematology, clinical chemistry and urinalysis. INR only for patients taking warfarin.

m) To perform only for pre-menopausal women or women who are amenorrhea for less than 12 months from the last menstrual cycle.

n) Adverse events will be collected from the time subject signs informed consent form through the last visit. Serious adverse events will be collected through the last visit and for 30 days after study termination.

o) The dose will be increased to 10 mg/day after confirmation of clinical response at Visit 8.

